4.2.2.5 Sensitivity Analyses of the Secondary Endpoint

Not applicable.

4.2.2.6 Supplementary Analyses of the Secondary Endpoint

Not applicable.

4.2.2.7 Subgroup Analyses

Not applicable.

4.2.3 Secondary Endpoint- Percent change in levels of LDL-C in serum

4.2.3.1 Definition

Percent change from baseline in LDL-C will be calculated on the raw scale for each subject. Reflex LDL-C will be primarily assessed and the direct LDL-C or other quantification may be considered in sensitivity analyses (refer to Section 4.2.1.1).

4.2.3.2 Derivations

LDL-C values will be assigned to analysis visits as defined in Section 3.3.2. Measurements below the LLOQ for which the exact value cannot be determined will be replaced by the LLOQ divided by the square root of 2.

LDL-C derived by Friedewald or Martin/Hopkins formula are indirectly calculated and hence may take 0 mg/dL or negative values (reported as ‘Unable to Calculate’ by Central lab) (Sampson et al, 2020). LLOQs will not be defined for these indirectly calculated measurements according to Central lab. These data will be replaced by 1/square root of 2 mg/dL for the analysis and displayed as reported from Central lab in the listings. After replacement of LLOQ, the percent change from baseline is calculated as the visit value minus the baseline value divided by the baseline value * 100.

4.2.3.3 Handling of Dropouts and Missing Data

Refer to Sections 4.2.1.3.

4.2.3.4 Analysis of Secondary Endpoint

LDL-C will be analyzed using the statistical model described for the primary endpoint (refer to Section 4.2.1.4).

LDL-C endpoints will be summarized by visit and treatment group using descriptive statistics (arithmetic mean, SD, minimum, median, maximum) using the principles defined in Section 3.3.

The plot of LSMean (95% CI) based on the MMRM estimates will be produced.

Percent change from baseline for direct LDL-C will be analysed similarly.

4.2.4 Secondary Endpoint- Levels of other lipid parameters

4.2.4.1 Definition

The following lipid parameters will be summarized:

- Total cholesterol (TC).
- High-density lipoprotein cholesterol (HDL-C).
- Non-HDL-C.
- Very low density lipoprotein cholesterol (VLDL-C).
- Apolipoproteins (Apo) A1.
- ApoB.
- Lp(a)
- Triglycerides.
- Remnants cholesterol.

4.2.4.2 Derivations

Refer to Section 4.2.2.2.

4.2.4.3 Handling of Dropouts and Missing Data

Refer to Section 4.2.2.3.

4.2.4.4 Analysis of Secondary Endpoint

Other lipid endpoints will be summarized as continuous log-normal variables and based on the Full Analysis Set.

Change from baseline and percent change from baseline will be summarized by visit and treatment group using descriptive statistics (arithmetic mean, SD, minimum, median, maximum) using the principles defined in Section 3.3.

An MMRM assuming a normal distribution on percent change from baseline to week 12 will also be presented for each lipid endpoint.

The following plots by visit will be created by treatment group:

- Mean (SD) for absolute value.
- LSMean (95% CI) for percent change from baseline based on MMRM estimates.

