9.4.2 Efficacy

[Part B]

The analysis and presentation of efficacy and exploratory endpoints will be based on participants in the full analysis set.

For selected efficacy variables, if not specified otherwise, a mixed model for repeated measures will be fitted using log-transformed data and results transformed back to geometric mean ratios for the purpose of presentation and interpretation. The mixed model for repeated measures will include the relevant log-transformed baseline biomarker value as a covariate. Time point (visit number), treatment, and the interaction between time point and treatment will be included as factors. The response variable will be change from baseline in log-transformed biomarker value. The model will be fitted with an unstructured covariance structure, and the Kenward-Roger correction applied to obtain the degrees of freedom. Estimation of the treatment effect will be done for each visit after baseline. In case of issues when fitting the model to the data, a hierarchical model fitting procedure will be described in the statistical analysis plan.

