9.4.2.2 Secondary Endpoint(s)

[Part B]

Percent change from baseline in LDL-C in the original scale will be calculated for each participant and then compared between treatment groups using a mixed model for repeated measures.

The change from baseline of log-transformed PCSK9 will be fitted using a mixed model for repeated measures and least square mean differences between treatment groups will be estimated from the fitted model. Results will be presented on the log scale and as geometric mean ratios.

Levels of other lipid parameters will be summarized using descriptive statistics.

Development of ADA will be monitored for each participant, analysis and reporting of data related to ADA will be specified in the statistical analysis plan.

For each treatment, the mean percentage change from baseline of LDL-C and PCSK9 levels will be plotted over time.

Pharmacokinetics

[Part A/Part C]

The PK analysis set will consist of all subjects in the safety analysis set who received AZD8233 and who have evaluable PK data, with no important protocol deviations thought to impact on the analysis of the PK data.

The exclusion of any subjects or time points from the calculation of the PK parameters will be documented by the PK scientist, including the reason(s) for exclusion.

The available concentration data and PK parameter data for any subjects excluded from the PK analysis set will be listed only. Concentration data for subjects excluded from the PK analysis set will be presented in the individual figures of concentration versus time plots.

[Part B]

If data permits, a population PK model will be developed, possibly with the support of PK data from studies D7990C00001 and D7990C00002 and additional clinical studies with

AZD8233, using nonlinear mixed effects regression analysis in NONMEM. Furthermore, if data allows, the population PK model may be coupled with separate PD models for PCSK9 and LDL-C.

All PK/PD modelling will be described in a separate data analysis plan. Moreover, the results of any such modelling will be provided in a separate population PK/PD report (as an appendix to the CSR or as a stand-alone report).

Plasma concentration data of AZD8233 will also be summarized by descriptive statistics per sampling time point in the CSR.

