2 CHANGES TO PROTOCOL PLANNED ANALYSES

1. 4.1 Study Population: Change from ‘Safety Analysis Set’ to ‘Full Analysis Set’ for summary of demographic data.
2. 9.4.2.1 Primary Endpoint (s): Regarding pair-wise comparisons, revised the description from ‘high’ to ‘mid’.
3. 9.4.2.2 Secondary Endpoint (s): The analysis of levels of other lipid parameters has been updated to include an analysis using MMRM.

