4.2.2.2 Derivations

PCSK9 measurement will be assigned to analysis visits as described in Section 3.3.2. Measurements below the LLOQ for which the exact value cannot be determined will be replaced by the LLOQ divided by the square root of 2. After replacement of LLOQ, the absolute change and percent change from baseline are calculated for each study visit.

Change from baseline of the log-transformed variable is calculated as the visit value in natural logarithm minus the baseline value in natural logarithm. Percent change from baseline is calculated using the raw values as the visit value minus the baseline value divided by the baseline value *100.

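### SAP Part B 4.2.4.4 treats the other lipids as log-normal but models only raw percent change with normal errors; a log-scale MMRM should be added

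*SAP*

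**What the plan says.** SAP Part B 4.2.4.4 opens with a distributional statement: "Other lipid endpoints will be summarized as continuous log-normal variables and based on the Full Analysis Set". It then lists descriptive statistics built on arithmetic means, and adds one model: "An MMRM assuming a normal distribution on percent change from baseline to week 12 will also be presented for each lipid endpoint". A plot of LSMeans with 95% intervals from that model follows. The endpoint table in SAP Part B 4.2 names the between-treatment LSMean difference at Week 12 as the population-level summary for this objective.

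The derivations in 4.2.4.2 point back to 4.2.2.2, where the log change is already defined: "Change from baseline of the log-transformed variable is calculated as the visit value in natural logarithm minus the baseline value in natural logarithm". So the log change is derived for these lipids, but no model uses it. The primary LDL-C endpoint (4.2.1.4) and PCSK9 (4.2.2.4) both have an MMRM on log change. For each of them the percent-change model is an addition to a log-scale model.

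The protocol plans less for these endpoints. Section 9.4.2.2 says: "Levels of other lipid parameters will be summarized using descriptive statistics". Its general efficacy rule in 9.4.2 reads: "For selected efficacy variables, if not specified otherwise, a mixed model for repeated measures will be fitted using log-transformed data". SAP Part B section 2, item 3, declares the addition but not the scale: "The analysis of levels of other lipid parameters has been updated to include an analysis using MMRM".

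**The concern.** Two statements in one section do not fit together. If a lipid is log-normal at baseline and on treatment, its ratio to baseline is log-normal too. Percent change is then right-skewed, and its standard deviation is proportional to the arm's mean ratio. An arm in which the lipid halves has half the spread of an unchanged arm.

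The primary model in 4.2.1.4 uses one unstructured covariance with no separate matrix by arm, and 4.2.4.4 names no alternative. A common variance averages the wide placebo arm with the narrow active arms. Placebo intervals then come out too short and active-arm intervals too long. The comparison between doses is tested against a variance inflated by placebo. At stake are the plotted 95% intervals and the between-arm intervals for the nine listed lipids, which are the only model-based results planned for them.

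**Working it through.** **Inputs.** Protocol 9.2 gives, for LDL-C, a log-scale SD of 0.3, 18 evaluable per arm, two-sided 5%, a difference of 0.693 versus placebo, a difference of 0.33 between doses, and 10% drop-out. No SD or effect is given for the other lipids. I therefore assume SD 0.3, show 0.4 and 0.5 as a range, and take mean ratios to baseline of 0.5, 0.7 and 0.8 as illustrations.

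**The plan's own figures first.** The standard error of a difference is 0.3 × √(2/18) = 0.10. For 0.33 the noncentrality is 3.3, and the t-test with 34 df has power 89.4% (stated: about 89%). For 0.693 power exceeds 99.9% (stated: more than 95%). 54/(1 − 0.10) = 60. All reproduce.

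**Spread of percent change by arm.** With log SD s and geometric mean ratio r, the SD of percent change is 100 × r × exp(s²/2) × √(exp(s²) − 1).

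- Placebo, r = 1, s = 0.3: 100 × 1.046 × 0.307 = 32.1 points.
- Active, r = 0.5: 16.05 points.

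**What a common variance does, both doses at r = 0.5.** Pooled SD = 32.1 × √((1 + 0.25 + 0.25)/3) = 22.7. The t quantile with 51 df is 2.008.

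- Placebo LSMean: model SE 22.7/√18 = 5.35, true SE 32.1/√18 = 7.57. Coverage ≈ P(|Z| < 2.008 × 5.35/7.57 = 1.42) ≈ 84%.
- Active LSMean: true SE 16.05/√18 = 3.78. Coverage ≈ P(|Z| < 2.84) ≈ 99%.
- Active minus placebo: model SE 22.7 × √(2/18) = 7.57, true SE √(7.57² + 3.78²) = 8.46. Coverage ≈ P(|Z| < 1.80) ≈ 93%.

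Simulation (three arms, 18 each, pooled variance, single visit, 40,000 trials) includes the skewness that this normal approximation omits. It gives 83%, 99% and 91.6% respectively. The log-scale interval for active versus placebo covers 95.0%.

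**Dose versus dose, ratios 0.5 and 0.7.** The log difference is ln(0.7/0.5) = 0.336, close to the protocol's 0.33.

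- Raw: difference 100 × 1.046 × 0.2 = 20.9 points. Pooled SD = 32.1 × √((1 + 0.25 + 0.49)/3) = 24.4, so the model SE is 8.15. The true SE is 32.1 × √((0.25 + 0.49)/18) = 6.51. Power ≈ P(Z > (2.008 × 8.15 − 20.9)/6.51) = P(Z > −0.70) ≈ 76%.
- Log: 0.336/0.10 = 3.36, so power ≈ P(Z > 2.008 − 3.36) ≈ 91%.

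| Log SD (assumed) | Raw power, simulated | Log power, simulated |
|---|---|---|
| 0.3 | 77% (76% on a repeat run) | 91% |
| 0.4 | 46% | 70% |
| 0.5 | 28% | 51% |

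**Milder effect, both doses at 0.8, SD 0.3.** Coverage is about 94% for active versus placebo and 91% for the placebo LSMean. In a two-arm t-test, power against placebo is 56.5% raw and 58.3% log.

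**The case against.** Three stronger readings are tempting, and the documents do not support them.

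- **That the raw model biases the mean upward.** It targets the arithmetic mean percent change and estimates that without bias: in simulation at ratio 0.5 and SD 0.3 the treatment difference was −52.35 points against a true −52.30. The arithmetic mean does exceed the geometric mean, by a factor exp(s²/2), which is +2.0% to +13.3% in an unchanged arm for assumed SDs of 0.2 to 0.5. This is a different summary measure. It cancels between arms when there is no effect, and simulated type I error is 4.8% to 4.9%.
- **That the SAP departs from an analysis the protocol specified.** The protocol planned only descriptive statistics here. Its log-scale rule covers selected variables and yields to other specifications, and the SAP declares the added MMRM. Protocol 9.4.2.2 itself plans an original-scale percent-change MMRM for LDL-C. At most, the added model does not follow the protocol's usual scale, and SAP section 2 is silent on scale.
- **That the results cannot be compared with LDL-C and PCSK9.** Percent-change MMRMs are planned for both (4.2.3.4 and 4.2.2.4), so percent change is the one scale common to all lipids. This is a good reason to keep the raw model.

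It is also fair to say that the endpoints are unpowered, that log-scale descriptive summaries are already foreseen, and that power against placebo is essentially unchanged at ratio 0.8. All of that stands. None of it explains why these lipids alone have no log-scale model, or repairs the intervals when effects are large.

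**Conclusion.** The inconsistency is real and its consequence is limited to interval calibration and dose-versus-dose precision. For lipids that fall about as far as the 50% assumed for LDL-C, the placebo interval is clearly too short, the active intervals too long, and the active-versus-placebo interval modestly too short. For reductions near 20% little is lost.

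The conclusion assumes log-normal ratios with equal log SD across arms, 18 per arm, and the primary model's single covariance carried over to 4.2.4.4, which does not state its own. The check uses one visit without baseline adjustment, not the full MMRM. The coverage figures hardly depend on the assumed SD, because the ratio of arm spreads equals the ratio of arm means whatever s is; the power figures do depend on it. The dose-versus-dose figures matter only if the comparison made for reference in 4.2.1.4 is repeated for these lipids. Severity is minor: these are secondary, unpowered endpoints.

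**What to change.** In SAP Part B 4.2.4.4, add an MMRM on change in the log-transformed lipid with log baseline as covariate, specified as in 4.2.1.4. Report 100 × (exp(LSMean) − 1) by arm and geometric mean ratios between arms, each with a 95% CI, as the main model result. Keep the raw percent-change MMRM as supplementary, for reading beside the LDL-C and PCSK9 percent-change analyses. In SAP section 2, item 3, state the scale of the added model.

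The cost is a few lines of SAP text and one more output per lipid. The log change is already derived, the primary model code can be reused, and no new data are needed.

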4.2.5 Secondary Endpoint- PK

4.2.5.1 Definition

Not applicable.

4.2.5.2 Derivations

Population PK parameters are not derived and analysed within this SAP. Details on population PK analysis are provided in a separate report prepared by a dedicated pharmacometrics support group at AstraZeneca. Plasma concentrations are evaluated descriptively.

4.2.5.3 Handlings of Dropouts and Missing Data

PK concentrations will be assigned to analysis visits as defined in Section 3.3.2. PK concentrations below the LLOQ for which the exact value cannot be determined, will be replaced with the LLOQ.

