The screening period starts within 28 days before the randomization visit and ends on Day -4. Eligible participants will make 7 visits during the treatment period and 7 additional visits during the follow-up period. They are randomized across 3 different treatment arms in a 1:1:1 ratio for a 12-week treatment period. The planned treatment arms are AZD8233 **CCI** , AZD8233 **CCI** , and placebo. Participants will be dosed subcutaneously on Days 1, 29, and 57.

Disclosure Statement:

[Part A/Part C]

This study is single-blind with regards to treatment (AZD8233 or placebo), and blinded to the participants, site investigators, and site staff. The Sponsor will be unblinded to treatment allocation.

[Part B]

This is a parallel group treatment study in 3 arms with participants, investigators and the sponsor blinded.

Number of Participants:

[Part A/Part C]

Approximately 11 participants will be randomly assigned to the 2 study arms in each part.

[Part B]

Approximately 60 participants will be randomly assigned to the 3 study arms.

Note: “Enrolled” means a participant's, or their legally acceptable representative's, agreement to participate in a clinical study following completion of the informed consent process.

Potential participants who are screened for the purpose of determining eligibility for the study, but are not randomly assigned/assigned in the study, are considered “screen failures”, unless otherwise specified by the protocol.

Study Period:

[Part A/Part B/Part C]

Estimated date of first patient enrolled: Q4 2020

Estimated date of last patient completed: Q4 2023

Intervention Groups and Duration:

[Part A/Part C]

The screening period starts up to 28 days before the randomization visit and ends on Day -4. Eligible participants will make 8 visits during the treatment period and 8 additional visits during the follow-up period. They are randomized across 2 different treatment arms at an 8:3 ratio for a 58-day (up to Visit 9) treatment period. The planned treatment arms are AZD8233 **CCI** (Part A) / AZD8233 **CCI** (Part C) and placebo. Participants will be dosed subcutaneously on Days 1, 8 (Part A only), 29, and 57.

[Part B]

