- a Weight should be measured in light indoor clothes, without shoes, after using the bathroom. Otherwise, follow the local standard procedure.
- b Injection Site Reaction assessments to be collected based on adverse event collection criteria.
- c Vital signs and ECG to be measured pre-dose on dosing days.
- d Blood samples for complement activation panel will be taken around C_{max} and are to be collected pre-dose and 2 hours (± 5 minutes) post-dose.
- e Samples to be obtained pre-dose on dosing days.
- f PK sampling to be performed at Visits 4 (Day 8), 6 (Day 29), 7 (Day 43), 8 (Day 57), 9 (Day 71), 10 (Day 85), 12 (Day 113), 14 (Day 141), and final follow-up visit/EDV. Schedule of sampling for Visit 6 (Day 29), 8 (Day 57) is shown below.
Visit 6 (Day 29): pre-dose, Visit 8 (Day 57): pre-dose.
- g ADA sampling to be performed at Visits 3 (D 1), 4 (D 8), 6 (D 29), 8 (D 57), 10 (D 85), 12 (D 113), 14 (D 141), and final follow-up visit/EDV. ADA samples to be collected pre-dose on all dosing days.
- h If, for any reason, the sample is not drawn pre-dose on Visit 3 (Day 1), it may be taken at any visit until the final follow-up/EDV visit.
- i Check screening labs and inclusion/exclusion criteria.
- j ECG to be performed during the follow-up period at Visits 10 (Day 85), 11 (Day 99), 13 (Day 127), and 15 (Day 155).
- k Pregnancy test: Serum β -human chorionic gonadotropin (β -hCG) will be performed on all the women participants, irrespective of childbearing potential.
- l Pregnancy test (Day 1): Urine pregnancy test using dipstick will be performed before randomization on all the women participants, irrespective of childbearing potential, at a local laboratory.
- m All the women participants should have FSH and LH levels determined, irrespective of childbearing potential.
- n In the case of early discontinuation, follow-up visit will be performed every 2 weeks after last dose.

[Part C]

Randomization should only proceed if all required assessments have been performed and all inclusion/exclusion criteria as well as other protocol restrictions have been evaluated; see Sections [5](#) and [6.5](#).

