4.2 Scientific Rationale for Study Design

AstraZeneca is developing AZD8233 for the treatment of dyslipidemia. This study consists of Part A, Part B and Part C. The objective of Part A is to investigate the safety and tolerability of AZD8233 following SC administration of multiple doses in a limited number of Japanese participants with dyslipidemia before progressing to Part B where a larger number of participants will be exposed. The study will also investigate the PK and the PD of AZD8233. Part B aims to evaluate the effect of different doses of AZD8233 on LDL-C at steady state to select a therapeutic dose for further clinical development. The objective of Part C is to investigate the safety and tolerability of **CCI** AZD8233 following SC administration of multiple dose (QM dosing) in a limited number of Japanese participants with dyslipidemia before progressing to Ph3. The study will also investigate the PK and the PD of AZD8233.

The dosing schedule (dosing on Days 1, 8 [Part A only], 29, and 57) should be sufficient to closely reach steady state conditions in the tissues at the end of the dosing period (the

estimated terminal half-life of the full length ASO in plasma is 2 to 3 weeks). Based on these data and the expected time course for PCSK9 and LDL-C reduction, the dosing schedule is predicted to allow for a robust assessment of safety, tolerability, PK, as well as PCSK9 and LDL-C reduction to guide dose selection for further clinical development of AZD8233.

The dosing and follow-up schedule are selected based on the long estimated terminal half-life of the full length AZD8233 ASO in plasma as well as the observed time course for PCSK9 levels to return to baseline after single dose administration in humans. Monthly dosing is predicted to result in a low level of fluctuation of PCSK9 levels and tissue exposure during a dose interval.

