4.2.5.2 Derivations

The geometric mean is calculated as the exponential of the arithmetic mean calculated from the data on the natural log scale.

The percent coefficient of variation is calculated as: $CV (\%) = \sqrt{(\exp(s^2) - 1)}$ where s is the standard deviation of the data on a log scale.

Handling of values below the lower limit of quantification (BLQ)

Plasma concentrations below the limit of quantification (BLQ) from the time of pre dose sampling (t = 0) up to the time of the first quantifiable concentration will be set to a value of 0. After the first quantifiable concentration, BLQ plasma concentrations will be set to missing for the calculation of PK parameters unless it is considered to be a true characteristic of the profile of the drug.

If two or more consecutive BLQ concentrations are followed by quantifiable concentrations in the terminal portion of the concentration curve, the profile will be deemed to have terminated and therefore these quantifiable values will be set to missing for the calculation

of the PK parameters unless there is a scientific rationale not to do so, which will be documented in the CSR.

Any embedded BLQ value (between two quantifiable concentrations) will be set to missing for the PK analysis.

If an entire concentration-time profile is BLQ, the profile is excluded from the PK analysis.

For descriptive statistics plasma concentrations that are below the LLOQ will be handled as follows:

- At a time point where less than or equal to 50% of the values are BLQ, all BLQ values will be set to LLOQ, and all descriptive statistics will be calculated.
- At a time point where more than half of the values are BLQ, the mean, SD, geometric mean and CV% will be set to Not Determined (ND). The max value will be reported from the individual data, and the min and median will be set to BLQ.
- If all values are BLQ at a time point, no descriptive statistics will be calculated for that time point. Not applicable (NA) will be written in the field for SD and CV% and BLQ will be written in fields for mean, geometric mean, min, median, and max.
- The number of BLQ values (n below LLOQ) will be reported for each time point.
- Where there is no result, these will be set to missing.

Urine concentrations that are below the LLOQ will be handled as follows:

- BLQ values should be set to zero for the calculation of individual Ae.

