4.2.5.4 Analysis of Secondary Outcome

Plasma concentrations will be summarized by each analysis visit and scheduled time using descriptive statistic, number of non-missing observations, n below LLOQ, arithmetic mean, SD, geometric mean, geometric coefficient of variation (CV%), min, median and max. Plasma concentrations will also be listed for all subjects in the PK analysis set.

4.2.6 Secondary Endpoint- Development of ADA and ADA titer (if subjects are ADA positive) during treatment and follow-up.

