4.2.5.2 Derivations

The geometric mean is calculated as the exponential of the arithmetic mean calculated from the data on the natural log scale.

The percent coefficient of variation is calculated as: $CV (\%) = \sqrt{(\exp(s^2) - 1)}$ where s is the standard deviation of the data on a log scale.

Handling of values below the lower limit of quantification (BLQ)

Plasma concentrations below the limit of quantification (BLQ) from the time of pre dose sampling ($t = 0$) up to the time of the first quantifiable concentration will be set to a value of 0. After the first quantifiable concentration, BLQ plasma concentrations will be set to missing for the calculation of PK parameters unless it is considered to be a true characteristic of the profile of the drug.

If two or more consecutive BLQ concentrations are followed by quantifiable concentrations in the terminal portion of the concentration curve, the profile will be deemed to have terminated and therefore these quantifiable values will be set to missing for the calculation of the PK parameters unless there is a scientific rationale not to do so, which will be documented in the CSR.

Any embedded BLQ value (between two quantifiable concentrations) will be set to missing for the PK analysis.

If an entire concentration-time profile is BLQ, the profile is excluded from the PK analysis.

For descriptive statistics plasma concentrations that are below the LLOQ will be handled as follows:

- At a time point where less than or equal to 50% of the values are BLQ, all BLQ values will be set to LLOQ, and all descriptive statistics will be calculated.

- At a time point where more than half of the values are BLQ, the mean, SD, geometric mean and CV% will be set to Not Determined (ND). The max value will be reported from the individual data, and the min and median will be set to BLQ.
- If all values are BLQ at a time point, no descriptive statistics will be calculated for that time point. Not applicable (NA) will be written in the field for SD and CV% and BLQ will be written in fields for mean, geometric mean, min, median, and max.
- The number of BLQ values (n below LLOQ) will be reported for each time point.
- Where there is no result, these will be set to missing.

Urine concentrations that are below the LLOQ will be handled as follows:

- BLQ values should be set to zero for the calculation of individual Ae.

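### SAP Part B has no rule for visits where most or all PK values are below the LLOQ, so at any such visit the tabulated means would be too high and the SD and CV% too small

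*SAP*

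**What the plan says.** SAP Part B section 4.2.5.3 gives one instruction for BLQ plasma concentrations: "PK concentrations below the LLOQ for which the exact value cannot be determined, will be replaced with the LLOQ". It applies whatever share of the values is BLQ. Under section 4.2.5.4 the concentrations are then "summarized by each analysis visit and scheduled time using descriptive statistic, number of non-missing observations, n below LLOQ", followed by "arithmetic mean, SD, geometric mean, geometric coefficient of variation (CV%), min, median and max".

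SAP Part A and SAP Part C handle the same problem in section 4.2.5.2 with graded rules:

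- With 50% BLQ or less, BLQ values are set to the LLOQ and all statistics are calculated, as in Part B.
- Above 50%, a second rule takes over: "where more than half of the values are BLQ, the mean, SD, geometric mean and CV% will be set to Not Determined"; the minimum and median are shown as BLQ and the maximum comes from the data.
- With all values BLQ, no statistics are calculated; SD and CV% are shown as NA and the other fields as BLQ.

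SAP Part B gives no reason for leaving out the second and third rules.

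**The concern.** Setting BLQ values to the LLOQ does limited harm when few values are affected. When most are, the substituted constant dominates the summary: the mean cannot fall below the LLOQ however low the true level is, and the spread shrinks because most entries are identical. Part B samples long enough after dosing for this to matter, and its highest dose is capped below the Part A dose (Protocol section 4.3), so BLQ values are at least as likely there as in Part A. The three parts would then report late concentrations of the same drug on different terms, and the part without the safeguard is the dose-ranging one.

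**Working it through.** The documents state no figure on this point, so there is none to reproduce. The check has two steps.

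**1. How late is the sampling?** In Part B, "Participants will be dosed subcutaneously on Days 1, 29, and 57" (Protocol section 1.1). The late PK samples are at Visits "10 (Day 85), 12 (Day 113), 14 (Day 141), and final follow-up visit/EDV" (Table 2, footnote f), and the final visit is Day 169. Protocol section 4.2 states that the "estimated terminal half-life of the full length ASO in plasma is 2 to 3 weeks", that is 14 to 21 days.

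Half-lives since the last dose = (day − 57) / half-life. Fraction left, relative to the start of the terminal phase after the Day 57 dose = 0.5^(number of half-lives).

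| Day | Days since dose | Half-lives (21 d / 14 d) | Fraction left (21 d / 14 d) |
|---|---|---|---|
| 85 | 28 | 1.3 / 2.0 | 40% / 25% |
| 113 | 56 | 2.7 / 4.0 | 15.8% / 6.3% |
| 141 | 84 | 4.0 / 6.0 | 6.3% / 1.6% |
| 169 | 112 | 5.3 / 8.0 | 2.5% / 0.4% |

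From Day 85 to Day 169 the level falls 16-fold (21 d) to 64-fold (14 d). Whether that crosses the LLOQ cannot be worked out, because no document gives the LLOQ or the expected late concentrations.

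**2. What does the substitution do if most values are BLQ?** Assumptions: lognormal concentrations, LLOQ scaled to 1, 20 participants per active arm (60 / 3), and a range of BLQ fractions and true CVs. Simulated results at a true CV of 50%:

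| BLQ | True mean → tabulated | SD, tabulated / true | Geometric CV, true → tabulated |
|---|---|---|---|
| 60% | 0.99 → 1.18 | 0.73 | 50% → 24% |
| 75% | 0.81 → 1.09 | 0.60 | 50% → 17% |
| 90% | 0.61 → 1.03 | 0.40 | 50% → 9% |

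Over true CVs of 30% to 80%, the SD ratio runs from 0.65 to 0.83 at 60% BLQ, 0.51 to 0.72 at 75%, and 0.31 to 0.53 at 90%.

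The geometric mean has a closed form. Let p be the BLQ fraction, σ the log SD, c = Φ⁻¹(p) and E = c·p + φ(c). The geometric mean is overstated by the factor exp(σE), stands at exp(σ(E − c)) times the LLOQ, and the log SD becomes σ·√(c²p + (1 − p) + cφ(c) − E²). With σ assumed to be 0.8:

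- p = 0.60: c = 0.253, E = 0.538. Overstated by exp(0.8 × 0.538) = 1.54; stands at exp(0.8 × 0.285) = 1.26 × LLOQ; log SD 0.80 → 0.40.
- p = 0.80: c = 0.842, E = 0.953. Overstated by exp(0.8 × 0.953) = 2.14; stands at exp(0.8 × 0.112) = 1.09 × LLOQ; log SD 0.80 → 0.24.

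If every value is BLQ, no model is needed: all entries equal the LLOQ, so the mean is the LLOQ and the SD is 0.

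**The case against.** The case for leaving the text alone has four parts.

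- **No visit is shown to have a BLQ majority.** Elapsed half-lives show decline, not position relative to an unknown LLOQ. This stands, and it makes the point conditional.
- **The censoring is visible.** The BLQ count is printed with the mean, all concentrations are listed, and with more than half BLQ the minimum and median both equal the LLOQ. This stands as mitigation, but the printed mean, SD and CV% remain biased.
- **Little depends on these tables.** SAP Part B section 4.2.5.2 leaves population PK to a separate report, and the Part B PK section plans no mean concentration plot and derives no terminal slope. The LDL-C analyses do not use PK values. A reader might infer that the substitution flattens an estimated terminal decline, but nothing planned in this SAP estimates one from these summaries. Section 4.2.6.4 does plan boxplots of PK concentrations by antibody status. It does not say how BLQ values enter them, and a rule on tabulated statistics would not change them.
- **Parts A and C are a different kind of study.** They use dense sampling and noncompartmental parameters; Part B samples sparsely. That could justify different PK methods, but it does not explain why a mean made up mostly of substituted values should be reported in one part and withheld in the others. The difference is nevertheless limited: at 50% BLQ or less, all three parts use the same substitution.

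**Conclusion.** The point holds in conditional form and is minor. SAP Part B lacks the majority-BLQ and all-BLQ rules of its sister plans. At any visit where they would apply, the mean and geometric mean are biased upward and the SD and CV% understated. The size depends on the BLQ fraction and the true spread, both assumed here: at 75% BLQ the SD is 0.51 to 0.72 of its true value for CVs of 30% to 80%. Only when all values are BLQ does the table show a mean equal to the LLOQ with an SD of 0.

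A reader might go further and infer that the late follow-up means do sit at the assay limit with almost no spread. The documents do not support that. A BLQ majority at Days 141 to 169 is plausible but not established. Even with one, the geometric mean is 1.26 times the LLOQ at 60% BLQ and 1.09 times at 80% (log SD 0.8), and the log SD is still 0.40 and 0.24. The consequence is confined to the descriptive PK summaries; the LDL-C analyses and the separate population PK report are not affected.

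**What to change.** Add both Part A/C rules to SAP Part B section 4.2.5.3:

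- If more than 50% of values at a visit are BLQ, report mean, SD, geometric mean and CV% as ND, minimum and median as BLQ, and the maximum from the data.
- If all values are BLQ, calculate no statistics: show SD and CV% as NA and the other fields as BLQ.

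Both rules are needed, because the first takes the maximum from the data and an all-BLQ visit has no quantifiable maximum. Visits with 50% BLQ or less are unchanged. The cost is one or two sentences and a small change to the table program; no data collection is affected.
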